6.13.6.5 Evaluations in Creatine Phosphokinase (CPK)

The planned summaries are provided in [Table JAIA.6.15](#).

Table JAIA.6.15. Summary Tables Related to Effects on CPK

Analysis
Shift tables showing the number and percentage of patients based on baseline to maximum during the analysis period will be created, with baseline depicted by the most extreme CTCAE grade during the baseline period. With each shift table, a summary displaying the number and percentage of patients who decreased, increased, or stayed the same in CTCAE grade category will be presented.
The number and percentage of patients with treatment-emergent shifts at any time during the analysis period, based on any increase to CTCAE Grade 1 or above, Grade 2 or above, Grade 3 or above, Grade 4 and above.
Treatment-emergent adverse events potentially related to muscle symptoms may also be analyzed based on reported AEs. The Muscle Symptoms special search category is a predefined MedDRA search criteria list that contains the narrow scope terms from the Rhabdomyolysis/myopathy SMQ (code 20000002) plus selected terms from the Musculoskeletal SOC.

Abbreviations: AE = adverse event; CPK = creatine phosphokinase; CTCAE = Common Terminology Criteria for Adverse Events, MedDRA = Medical Dictionary for Regulatory Activities; SMQ = Standardized MedDRA Query; SOC = System Organ Class.

6.13.6.6 Infections

Infections will be defined using all the PTs from the MedDRA Infections and Infestations SOC. The MedDRA terms used to identify infections considered to be opportunistic infections (OIs) are based on Winthrop et al. 2015 and are listed in the compound level safety standards. The list contains narrow (more specific) and broad (less specific) PTs.

The planned summaries are provided in [Table JAIA.6.16](#).

Table JAIA.6.16. Summary Tables Related to Infections

Analysis
The number and percentage of patients with treatment-emergent infections, serious infections, and infections resulting in permanent study drug discontinuation using MedDRA PTs
The number and percentage of patients with TEAEs of infections by maximum severity using MedDRA PTs
Listing of patients experiencing TEAE infections will be provided. The listing will include patient demographics, treatment group, treatment start and stop dates, infectious PT event, infecting organism(s), event start and stop dates, total leukocytes, total lymphocytes, absolute neutrophils, event seriousness, and event outcome.
Summary of Opportunistic Infections based on MedDRA PTs after the potential opportunistic infections are reviewed by medical and confirmed as opportunistic infections.
Listing of Opportunistic Infections based on MedDRA PTs during the study.
The summary table of herpes simplex will include event maximum severity, seriousness, whether resulting in temporary study drug interruption, whether resulting in study drug discontinuation, whether treated with antiviral medication and event outcome.
A summary table of herpes zoster will be provided, including event maximum severity, seriousness, whether resulting in temporary study drug interruption, whether resulting in study drug discontinuation, whether treated with antiviral medication, and event outcome. The incidence rate will also be provided.
A listing of patients with detectable HBV DNA include patient demographics, treatment group, visit, lab sample dates, baseline serology.
Hepatitis B virus DNA status (not detectable, detectable but not quantifiable [i.e., < lower limit of detection (LLOD)], quantifiable [i.e., ≥LLOD]) stratified by applicable baseline HBV serology status (HBsAb- / HBcAb-, HBsAb+ / HBcAb-, HBsAb+ / HBcAb+, HBsAb- / HBcAb+)

Abbreviations: HBV = hepatitis B virus; MedDRA = Medical Dictionary for Regulatory Activities; PT = preferred term; TEAE = treatment emergent adverse event.

6.13.6.7 Allergic Reactions and Hypersensitivities

A search for relevant events related to allergic reaction and hypersensitivity will be performed using the following SMQs:

- Anaphylactic reaction SMQ (20000021)
- Hypersensitivity SMQ (20000214)
- Angioedema SMQ (20000024)

The planned summaries are provided in [Table JAIA.6.17](#).

The anaphylactic reaction SMQ consists of a narrow search containing PTs that represent core anaphylactic reaction terms, a broad search that contains additional terms (signs and symptoms possibly indicative of anaphylactic reaction) that are added to those included in the narrow search, and an algorithm.

The algorithmic approach (Algorithm 1), which is similar to the algorithm approach defined in Sampson, et al. 2006, comprises 1 or more events associated with an individual administration of study drug, where the events include:

- A narrow term from the anaphylactic reaction SMQ (Category A of the SMQ) or
- Paired terms from the anaphylactic reaction SMQ, comprising terms from at least 2 of the following 3 categories from the SMQ:
 - Category B - (Upper Airway/Respiratory signs and symptoms)
 - Category C - (Angioedema/Urticaria/Pruritus/Flush signs and symptoms)
 - Category D - (Cardiovascular/Hypotension signs and symptoms).

Within the paired terms approach, it is important to recognize that occurrence of these events should be nearly coincident and develop rapidly after exposure to an antigen; a window wherein onset or severity change of the events occur within the same calendar day will be used.

In addition, a second algorithmic approach (Algorithm 2) will be calculated similarly to the algorithm approach defined above (Algorithm 2) but includes an additional category, Category E. The paired terms according to Algorithm 2 will comprise terms from at least 2 of 4 categories (Categories B, C, D, and E). Categories B, C and D are already defined, and Category E includes any of the Gastrointestinal preferred term events (Nausea, Vomiting, Diarrhoea, and Abdominal pain). A patient's listing will be generated based on Algorithm 2 and individual cases will be examined to determine if the cases suggest anaphylaxis. Those cases suggestive of anaphylaxis will be described in CSR.

Table JAIA.6.17. Summary Tables Related to Allergic Reactions/Hypersensitivities

Analysis

Two listings for Allergic Reaction and Hypersensitivities for events that satisfy the queries defined in this section will be listed, by temporal order within patient ID, and will include SOC, PT, SMQ event categorization including detail on the scope (narrow, algorithmic, or broad), reported AE term, AE onset and end dates, severity, seriousness, outcome, etc.

The number and percentage of patients reporting a TEAE for the following will be analyzed:
 
 • Any narrow or algorithmic term (Algorithm 1) from any one of the 3 SMQs indicated above (i.e., combined search across narrow portions of all 3 SMQs, and anaphylaxis algorithm for Anaphylactic reaction SMQ) • Any narrow scope term within each SMQ, separately (i.e., narrow SMQ search) • Any term within each SMQ, separately (i.e., broad SMQ search)

Abbreviations: AE = adverse event; ID = identification; PT = preferred term; SOC = system organ class; SMQ = Standardized MedDRA Query; TEAE = treatment emergent adverse event.

6.13.6.8 Major Adverse Cardiovascular Events (MACE) and Other Cardiovascular Events

Major adverse cardiovascular events (MACE) and other cardiovascular events will be adjudicated by an independent, external adjudication committee. All confirmed events after adjudication will be used for the analysis.

The planned summaries are provided in [Table JAIA.6.18](#).

Table JAIA.6.18. Summary Tables Related to MACE and Other Cardiovascular Events

Analysis
The number and percentage of patients with MACE, other cardiovascular events, non-cardiovascular death, and all-cause death, as positively adjudicated, based on the categories and subcategories as defined in compound level safety standards
A listing of the MACE and other CV sent for adjudication will be provided to include data concerning the MedDRA PT related to the event, the seriousness of the event, and the event outcome, along with the adjudicated result.

Abbreviations: CV = cardiovascular; MACE = major adverse cardiovascular event; MedDRA = Medical Dictionary for Regulatory Activities; PT = preferred term.

6.13.6.9 Thromboembolic Events

Venous thromboembolisms will be adjudicated by an independent, external adjudication committee. Venous and pulmonary artery thromboembolic events will be classified as deep vein thrombosis (DVT), pulmonary embolism (PE), or other peripheral venous thrombosis. Additionally, arterial thromboembolic (ATE) events will be adjudicated by an independent, external adjudication committee. All confirmed events after adjudication will be used for the analyses.

The planned summaries for VTE related events are provided in [Table JAIA.6.19](#).

Table JAIA.6.19. Summary Tables Related to VTEs

Analysis
The number and percentage of patients with a positively adjudicated VTE, DVT, PE, and other peripheral venous thrombosis.
A listing of the VTEs sent for adjudication, to include data concerning the MedDRA PT related to the event, the seriousness of the event, and the event outcome, along with the adjudicated result

Abbreviations: DVT = deep vein thrombosis; MedDRA = Medical Dictionary for Regulatory Activities; PE = pulmonary embolism; PT = preferred term; T = Treatment period; VTE = venous thromboembolism.

The planned summaries for ATE related events are provided in [Table JAIA.6.20](#).

Table JAIA.6.20. Summary Tables Related to ATEs

Analysis
The number and percentage of patients with a positively adjudicated ATE
A listing of the ATEs sent for adjudication to include data concerning the MedDRA PT related to the event, the seriousness of the event, and the event outcome, along with the adjudicated result

Abbreviations: ATE = arterial thromboembolic; MedDRA = Medical Dictionary for Regulatory Activities; PT = preferred term.

6.13.6.10 Malignancies

Malignancies will be identified using terms from the malignant tumors SMQ. Malignancies excluding nonmelanoma skin cancers (NMSC) and NMSC will be reported separately. All the cases identified by the malignant tumors SMQ (SMQ code = 20000194) will be assessed through medical review to determine *confirmed* NMSC cases. Refer to the compound-level safety standards for more details including the list of the planned NMSC terms.

The planned summaries are provided in [Table JAIA.6.21](#).

Table JAIA.6.21. Summary Tables Related to Malignancies

Analysis
The number and percentage of patients with treatment-emergent malignancies excluding NMSC, and NMSC
Listing of all malignancy cases, with an NMSC flag

Abbreviation: NMSC = nonmelanoma skin cancers.

6.13.6.11 Gastrointestinal Perforations

Potential GI perforations identified by the SMQ search (SMQ code = 20000107) will be provided as a listing for internal review by the medical safety team. Each case will be assessed to determine whether it is “confirmed” GI perforation. All confirmed events after medical review will be used for the analysis. The planned summaries are provided in [Table JAIA.6.22](#).

Table JAIA.6.22. Summary Tables Related to Gastrointestinal Perforations

Analysis
The number and percentage of patients with treatment-emergent gastrointestinal perforations using MedDRA PTs.
Listing of all treatment-emergent gastrointestinal perforations during the study.

Abbreviations: MedDRA = Medical Dictionary for Regulatory Activities; PT = preferred term.

6.13.6.12 Depression and Suicide

During the study, suicidal ideation and behavior, and depression will be assessed prospectively by the investigator via signs and symptoms and through the use of the C-SSRS and the QIDS-SR16. For self-harm events, the Self-Harm follow-up form is used to collect answers to a series of questions that provides a more detailed description of self-harm cases. The QIDS-SR16 total scores will also be categorized into severity classes (none, mild, moderate, severe, very severe). Refer to the compound level safety standards, and to Appendix 2 of the integrated safety analysis plan for more details for the QIDS-SR16 including documentation of errors by country and items needed to set to missing by statistical programming.

The planned summaries are provided in [Table JAIA.6.23](#).

Table JAIA.6.23. Summaries Related to Depression and Suicide

Analysis
A listing of the C-SSRS answers for patients with any “yes” answer
A listing of the responses given on the Self-Harm follow-up form
Number and percentage of C-SSRS binary responses and composite endpoints
Number and percentage of patients reporting suicidal ideation, suicidal behavior, and non-suicidal self-injurious behavior based on the C-SSRS during treatment
Shift analysis and Treatment-emergent changes in QIDS-SR16 total score

Abbreviations: C-SSRS = Columbia-Suicide Severity Rating Scale; QIDS-SR16 = Quick Inventory of Depressive Symptomatology Self Report.

6.14 Subgroup Analysis

6.14.1 Efficacy Subgroup Analyses

Subgroup analyses will be conducted for the primary endpoints SRI-4 at the Week 52 visit in the mITT population with PPCV datapoint set (Table JAIA.6.5) using hybrid imputation approach as in primary analysis (Section 6.4.2.4). Additional subgroup analyses may be conducted for the other important secondary endpoints if needed.

A logistic regression analysis with treatment, subgroup, and treatment-by-subgroup interaction as factors will be applied on each of 25 imputed datasets after the hybrid imputation. The treatment-by-subgroup interaction will be tested using the Firth correction (Firth 1993) at the 10% significance level. Treatment group differences will be evaluated within each subgroup using the Chi-square test on each of 25 imputed datasets after the hybrid imputation as well, regardless of whether the interaction is statistically significant. Then the single estimates from both logistic regression and Chi-square test for each imputed dataset will be combined using Rubin’s rules (Rubin 1987) via PROC MIANALYZE, respectively.

If any group within the subgroup (for example, yes, no) is <10% of the total population, only descriptive statistics will be provided for that subgroup (that is, no inferential testing).

Forest plots may be created to illustrate the treatment differences with 95% CIs between each of the baricitinib-2mg and 4mg treatment groups and placebo group, by each subgroup category.

The following subgroups will be analyzed:

- Disease severity at baseline (SLEDAI-2K): (<10; \geq 10)
- SLEDAI-2K organ system involvement at baseline (yes or no for each organ system domain)
- Gender: (Male; Female)
- Baseline anti-dsDNA status: (positive; negative)
- Baseline Complement: (low C3 and/or low C4 levels; high C3 and C4 levels)
- Baseline Low complement/anti-dsDNA positive: (low C3 and/or C4 levels, and anti-dsDNA positive; Others)
- Race: (American Indian/Alaska Native; Asian; Black/African American; Native Hawaiian or other Pacific Islander; White; Multiple)

- Ethnicity (US only): (Hispanic or Latino; Not Hispanic or Latino)
- Region: (North America; Central/South America/Mexico; Europe, Asia; Rest of World)
- Age (<40; \geq 40 years old)
- Age (<65; \geq 65 years old)
- Baseline corticosteroid dose (<10 mg/day; \geq 10 mg/day prednisone or equivalent)

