5.2 Determination of Sample Size

Study JAIA will randomize approximately 750 patients with a 1:1:1 ratio between baricitinib 4-mg, 2-mg, and placebo. The proposed sample size will ensure >90% power to detect an absolute difference of 17% between a baricitinib treatment group and the placebo treatment group assuming a 40% placebo response rate for the primary endpoint using a 2-sided α of 0.05. The anticipated effect size represents a clinically relevant difference.

Sample size and power estimates were obtained from nQuery® Advisor 7.0 using the χ^2 test of equal proportions.

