5.3 Method of Assignment to Treatment

Patients who meet all criteria for enrollment will be randomized in a 1:1:1 ratio (baricitinib 4-mg; baricitinib 2-mg; placebo) to double-blind treatment at Visit 2 (Week 0). Randomization will be stratified by disease activity (total Systemic Lupus Erythematosus Disease Activity Index 2000 [SLEDAI-2K] <10; \geq 10), corticosteroid dose (<10 mg/day; \geq 10 mg/day prednisone or equivalent at baseline), and region as given in [Table JAIA.5.1](#).

Assignment to treatment groups will be determined by a computer-generated random sequence using an IWRS. The IWRS will be used to assign packages containing double-blind investigational product to each patient, starting at Visit 2 (Week 0), and at each visit subsequent through Visit 15 (Week 48).

Table JAIA.5.1. Countries and Associated Geographical Regions

Geographical Region	Country or Countries
North America	United States
Central, South America and Mexico	Argentina, Chile, Colombia
Europe	France, Italy, Poland, Romania, Spain
Asia	Japan, Korea, Philippines
Rest of World	India, Serbia, South Africa

6 A Priori Statistical Methods

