6.4 Analysis Methods

The family-wise type I error rate (FWER) will be controlled at a 0.05 significance level for primary and major secondary endpoints using a prespecified graphical procedure (see Section 6.6). Unless otherwise specified, all other hypothesis testing will be conducted at a nominal significance level of 0.05.

For assessments of the primary endpoint and other binary efficacy and health outcomes endpoints, the following will be provided unless otherwise specified:

- Observed percentage for each treatment group along with the corresponding 2-sided 95% confidence interval (CI)
- The difference in percentages and 95% CI using the Newcombe-Wilson method without continuity correction, used for descriptive purposes
- The p-value and 95% (unless otherwise specified) CI for the odds ratio from the logistic regression model, used for primary statistical inference. The model will include the following explanatory variables: treatment, baseline disease activity (total SLEDAI-2K <10; ≥ 10), baseline corticosteroid dose (<10 mg/day; ≥ 10 mg/day prednisone or equivalent) and region (North America, Central/South America/Mexico, Europe, Asia and Rest of World). A Firth penalized likelihood will be used (Firth 1993), and
- If deemed necessary, additional analyses of categorical efficacy variables will be conducted to address sparse data or small sample sizes. The Fisher's exact test will be utilized if necessary.

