6.4.1 Adjustments for Covariates

Randomization is stratified according to disease activity (total SLEDAI-2K at screening <10; ≥ 10), corticosteroid dose at baseline (<10 mg/day; ≥ 10 mg/day prednisone or equivalent), and region (North America, Central/South America/Mexico, Europe, Asia and Rest of World). Therefore, these factors will be adjusted for as described in Section [6.4](#).

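### The SRI-4 subgroup analyses drop, without explanation, the stratification factors used in the primary model; if those factors are prognostic, interaction effects are attenuated and some power is lost

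*SAP*

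**What the plan says.** - **Randomisation (SAP 5.3).** "Randomization will be stratified by disease activity", by corticosteroid dose and by region (five levels).
- **Primary model (SAP 6.4).** For binary endpoints, "The model will include the following explanatory variables: treatment, baseline disease activity", then corticosteroid category and region, with a Firth penalty. This is a default that other sections may override.
- **Reason for adjusting (SAP 6.4.1).** Having listed the stratification factors, it concludes: "Therefore, these factors will be adjusted for as described in Section" 6.4.
- **Subgroups (SAP 6.14.1).** "A logistic regression analysis with treatment, subgroup, and treatment-by-subgroup interaction as factors will be applied on each of 25 imputed datasets". The interaction is tested with the Firth correction at the 10% level. Arms are then compared within each subgroup by chi-square, and both sets of results are pooled by Rubin's rules. Categories below 10% of the population are only described. No reason is given for leaving the strata out.
- **A restricted population elsewhere (Table JAIA.6.6, footnote g).** For patients on more than 7.5 mg/day prednisone at baseline, the logistic model drops the corticosteroid factor but keeps SLEDAI-2K category and region.
- **An unadjusted analysis elsewhere (SAP 6.10.3.3.1).** The tipping point analysis is unadjusted, and there a reason is given: Phase 2 data suggest that adjusted and unadjusted odds ratios will be close.

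**The concern.** The same endpoint, on the same 25 imputed datasets, is modelled with the strata for the main result and without them for the subgroups. An odds ratio is not collapsible: leaving out a prognostic covariate moves it toward 1 even when the arms are perfectly balanced. An unadjusted subgroup odds ratio and the adjusted primary odds ratio therefore estimate different quantities. The interaction log odds ratio shrinks in the same way, which costs the interaction test some power. The strata are already collected and already used in the imputation model, so leaving them out gains little.

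**Working it through.** **1. The plan's own figure.** Inputs from SAP 5.2: "Study JAIA will randomize approximately 750 patients with a 1:1:1 ratio", so about 250 per arm; "assuming a 40% placebo response rate for the primary endpoint using a 2-sided" alpha of 0.05; 40% against 57%; chi-square "test of equal proportions".

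Pooled rate = (0.40 + 0.57)/2 = 0.485. Null SE = √(2 × 0.485 × 0.515/250) = 0.0447. Alternative SE = √((0.40 × 0.60 + 0.57 × 0.43)/250) = 0.04405. Power = Φ((0.17 − 1.96 × 0.0447)/0.04405) = Φ(1.87) = 96.9%. The stated power above 90% is reproduced (180 per arm would suffice for 90%), and it does not depend on the subgroup model.

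**2. Simulation of the subgroup model.** The SAP gives no prognostic strengths, so these settings are assumptions:
- 2,000 trials per setting, two arms of 250, randomised within strata, marginal rates 40% and 57%.
- 50% of patients in the upper SLEDAI-2K category, 45% in the upper corticosteroid category, regions 20/20/30/20/10%.
- A subgroup of 40% that is not itself a stratification factor.
- SLEDAI-2K log odds ratio 0, 0.5, 1.0 or 1.5 (none, moderate, strong, very strong), with the other factors scaled in proportion.
- Ordinary maximum likelihood, without the Firth penalty.

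Each trial was analysed without and with the three strata as main effects.

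*No true interaction:*

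| Prognosis | SE without | SE with | Rejection at 10% without | Rejection at 10% with |
|---|---|---|---|---|
| None | 0.373 | 0.378 | 10.1% | 10.4% |
| Moderate | 0.373 | 0.384 | 9.9% | 10.2% |
| Strong | 0.373 | 0.399 | 10.0% | 10.2% |
| Very strong | 0.373 | 0.422 | 9.7% | 9.5% |

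*True interaction log odds ratio 0.8:*

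| Prognosis | Estimate (SE) without | Estimate (SE) with | Power without | Power with | Difference, points |
|---|---|---|---|---|---|
| None | 0.813 (0.380) | 0.822 (0.385) | 68.0% | 67.6% | −0.4 |
| Moderate | 0.778 (0.380) | 0.812 (0.390) | 64.7% | 66.4% | 1.7 |
| Strong | 0.735 (0.379) | 0.830 (0.406) | 61.9% | 66.3% | 4.4 |
| Very strong | 0.660 (0.378) | 0.824 (0.428) | 54.3% | 61.1% | 6.8 |

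The ratio of estimate to SE explains the pattern. Adjustment widens the SE, but it raises the estimate by more: 0.735/0.379 = 1.94 against 0.830/0.406 = 2.04 for strong prognosis, and 0.660/0.378 = 1.75 against 0.824/0.428 = 1.93 for very strong. The simulation error of one power figure is about √(0.65 × 0.35/2000) = 1.1 points. Both models were fitted to the same trials, so the differences are steadier than that. The −0.4 with no prognosis is a tie.

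**3. Scale.** Rates of 57% and 40% give an unadjusted odds ratio of (0.57 × 0.60)/(0.43 × 0.40) = 1.99, log 0.687. The conditional log odds ratios that produce the same two rates are 0.708, 0.766 and 0.854 for moderate, strong and very strong prognosis, that is odds ratios of about 2.03, 2.15 and 2.35. The same treatment effect thus yields different odds ratios from the two models.

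**4. Imbalance.** Within the 40% subgroup, the share in the upper SLEDAI-2K category differed between arms by 4.3 to 4.6 points on average in absolute value. At the plan's 10% threshold (75 of 750 patients, 25 per arm), a factor with 50% prevalence would differ by about √(2/π) × √(2 × 0.5 × 0.5/25) = 11 points, ignoring stratification. These differences are random in direction.

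**The case against.** Several stronger readings are tempting and fail.

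- **That the unadjusted analysis is less precise.** On the log-odds scale it is the reverse: the interaction SE is 0.373 without the strata and 0.378 to 0.422 with them. The cost is attenuation, not a wider interval.
- **That chance imbalance will produce spurious interactions.** Imbalance inside a subgroup is random, and the test already allows for it: unadjusted rejection under no interaction was 9.7% to 10.1%.
- **That Section 6.14.1 contradicts Section 6.4.1.** Section 6.4 is a default that allows exceptions, and 6.14.1 states one.
- **That subgroup odds ratios must sit below the primary one.** That holds only so far as the strata are prognostic.

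The defence also has fair points. For this endpoint the SAP expects adjusted and unadjusted odds ratios to be similar, which, if right, puts the trial near the none-to-moderate rows. That reason is offered only for the tipping point analysis, however, and 6.14.1 does not invoke it. The forest plots are planned for treatment differences; if these are differences in percentages, Section 6.4 supplies an unadjusted overall difference to set beside them. Each stratification factor is itself a listed subgroup, so it enters the model when tested, although the other two stay out. Finally, adjustment cannot be applied mechanically: ethnicity is analysed in US patients only, and Table JAIA.5.1 lists only the United States under North America, so region is constant there.

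**Conclusion.** The point holds as a minor one. The subgroup model omits strata that the primary model includes, and the SAP does not say why. The primary result, the sample size and the multiplicity-controlled tests are untouched, and the interaction test held its level. In the settings examined, the attenuation and the power loss ranged from nil, with strata that do not predict response, to 0.66 against 0.82 and 6.8 points with very strong ones. These sizes rest on assumed stratum effects, a single 40% subgroup and an assumed interaction of 0.8, without the Firth penalty. The difference in scale between subgroup and primary odds ratios follows from the two models whenever the strata are prognostic.

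**What to change.** In Section 6.14.1:

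- Add SLEDAI-2K category, corticosteroid category and region as main effects to the Firth interaction model. Leave out any factor that is itself the subgroup or is constant in the analysed set, such as region for the US-only ethnicity subgroup. Footnote g of Table JAIA.6.6 is a precedent for a reduced covariate set.
- Take within-subgroup odds ratios and their standard errors from that model and pool those. Rubin's rules need an estimate with a standard error, which a chi-square test does not by itself supply.
- Keep unadjusted percentage differences as a descriptive display.

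If the sponsor prefers the unadjusted analysis, one sentence giving the reason, and stating that subgroup odds ratios are not on the scale of the primary one, would meet the point.

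The cost is SAP wording and a little programming, with no new data. The downside is a wider standard error on the log-odds scale: in the no-interaction simulations by 0.378/0.373, about 1%, up to 0.422/0.373, about 13%.
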